6.3. Missing data

Missing data can occur from patient dropout (unit non-response), failure to provide data (item non-response), or administrative issues. We will minimize missing data by closely monitoring accumulating data for missingness and implementing procedures to reduce it when identified (MD-1⁶). The distribution of patients with missing data for each variable will be thoroughly investigated (MD-1⁵). When a patient drops out of the study, we will document the reason for dropout and who made the dropout decision (MD-4⁷). We will compare patients with complete data to those with missing data to assess potential biases. Our approach will depend on both the pattern and the magnitude of the missing data, following strategies recommended by PCORI methodology standards and the National Research Council. For example, we

⁵ Senn S. Testing for baseline balance in clinical trials. Stat Med. Sep 15 1994;13(17):1715-1726.

⁶ Describe methods to prevent and monitor missing data.

⁷ Describe how you will record and report all reasons for dropout and missing data, and account for all patients in reports.

will conduct sensitivity analyses (MD-5⁸) based on different assumptions (MD-2⁹, MD-3¹⁰) including multiple imputations.

Our specific plan for handling missing data with the MADRS (at baseline or endpoint) is as follows: for those missing a centrally-administered MADRS, we will accept a locally administered one. For MADRS missing at baseline or at endpoint in completers, we will impute a MADRS score. For those who stop Step 1 (acute) or Step 2 (acute) early, prior to week 10, and do not have a MADRS score, we will treat them as non-remitters with respect to the primary effectiveness analysis.

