Yet, in spite of the high stakes for public health, the comparative risk/benefit ratio of antidepressants is entirely unstudied in older adults with TRD. This stands in contrast with numerous studies in younger adults.²⁵⁻²⁹ This evidence gap was highlighted in critical reviews^{30,31}

that found a complete lack of evidence in this age group. The sole exception is our recent randomized controlled trial (RCT) of aripiprazole augmentation in older adults.^{2,32}

C Study Objectives

The study aims to close the evidence gap on late-life depression in three ways:

C1 Aim 1: Effectiveness

Examine the comparative benefits and risks of antidepressant strategies (augmentation and switching) in older adults with TRD.

Effectiveness outcomes: psychological well-being and remission from depression Safety outcomes: serious adverse events, falls, and fall-related injuries

C2 Aim 2: Effects of Aging

Explore how age, and age-related variables (medical comorbidity, cognitive problems) change the balance of benefits vs. risks.

C3 Aim 3: Maximize Stakeholder Engagement

We will maximize stakeholder engagement to ensure relevancy to providers and patients alike.

C4 Rationale for the Selection of Outcome Measures

OUTCOME	WHEN AND HOW MEASURED	RATIONALE
Psychological well-being is the patient-centered effectiveness outcome (Hypothesis 1a [H1a]).	In Acute, beginning and end of Step 1 (and Step 2); in Continuation months 4, 8, 12.	Psychological well-being encompasses satisfaction, happiness, cognitive engagement,
Secondary quality of life measures are self-reported physical function and social participation.	Measured by NIH Toolbox* (Psychological Well-being) and PROMIS* (Physical function, Social participation). Assessed by independent rater**	and meaning/purpose. It is a critical dimension of quality of life, recommended by patient stakeholders in focus groups as an outcome that matters.
Remission is our clinician- focused effectiveness outcome (H1b): reduction of depressive symptoms below a threshold (MADRS≤10). This goal of treatment is a consensus among practitioners. ^{53,54}	In Acute, beginning and end of Step 1 (and Step 2); in Continuation, months 4, 8, 12 Assessed by independent (blind) rater** via 20-30 minute phone interview.	The MADRS measures 10 areas of depressive symptoms. It is a standard outcome in antidepressant studies. Patient stakeholders described this assessment as "very important" for assessing effectiveness.

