Study sites will be responsible for developing their site-specific recruitment plans and obtaining IRB approval for the plan and all recruitment materials. In most cases, recruitment will be facilitated through partnerships with community mental health and primary care clinics. Plans for recruitment by referral or via a partial waiver of HIPAA authorization for recruitment purposes must be agreed upon by the appropriate community personnel, and approved by the local IRB, prior to implementing.

1.g Randomization Method and Blinding

Randomization of participants will be implemented in REDCap, using a randomized block design within clinic and age group using variable block size, stratified by institutional site and age strata.

Only assessors of outcome measures will be blinded. Participants, providers, and other research staff will not be blinded to participants' condition.

In this pragmatic design where all levels of adherence are allowed, participants will be considered randomized assuming they meet the eligibility requirements at screening (including any safety screens as applicable) and they and/or their clinician has been given a randomization assignment.

1.h Potential Risks

Study Instruments and measures: The assessments to be conducted as part of this study involving mood assessments, neuropsychological testing, and behavioral and functional assessments are non-invasive and carry with them no more than minimal risk. The most significant risks to the participants related to assessments are those that would follow a breach of confidentiality and the disclosure of clinical information. We also include discomfort in the potential risks. The instruments to be used in this study are brief and pragmatic and have been well-tolerated by older adults in other studies.

Aripiprazole: The most common side effect of aripiprazole (occur in 25% of people) is akathisia.

Common side effects (occur in 1-25% of people) include restlessness, insomnia, fatigue, blurred vision, somnolence, tremor, constipation, sedation, and dizziness. There is a potential that aripiprazole may increase the risk of hyperglycemia (increased blood sugar), diabetes, abnormal cholesterol or increased triglycerides.

We will monitor patients for these symptoms and require that they have a fasting blood glucose and lipid profile obtained prior to start of aripiprazole and as often as clinically necessary.

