Potential participants identified through each site's IRB-approved recruitment plans will be screened for eligibility. Staff and PI's at each site are responsible for verifying that participants at their site meet all eligibility criteria before being randomized to acute treatment. We anticipate differences between sites in which assessments may be obtained in pre-screening (pre- written consent) versus screening (post written consent). Despite these potential differences, the following assessments must be conducted prior to randomization to ensure eligibility (see also Section D2 for Inclusion and Exclusion Criteria):

- PHQ-9
- MINI MDE Module
- Screening questions for treatment resistance and medical exclusions
- Short Blessed Test
- ATHF
- CIRS-G

1.a **Screening Log**

Each site will use a phone screening script and screening log as approved by their IRB. In the event that participants do not currently qualify for the study, but may qualify in the near future, research staff will ask the potential participant for permission to keep their contact information on file and follow up with them and/or their doctor at a later date.

F2 Schedule of Measurements

OPTIMUM Revised 03/30/17 (Changes in Yellow)	Pre/ Screening	Baseline		:	Step 1 (10 weeks)					9	Step 2 (1	Continuation (12 months)					
Done by local sites:			wk0	wk2	wk4	wk6	wk8	Step end*	wk0	wk2	wk4	wk6		Step	manth 4	manth 0	month 12
PHQ-9	х		WKU	WKZ	WK4	WKO	WKO	enu	WKU	WKZ	WK4	WKO	WKO	ena	IIIOIILII 4	IIIOIILII 6	IIIOIILII 12
Sociodemographics	X																
Screening questions for treatment resistance and medical exclusions	X																
Short Blessed Test	x																
Consent		х															
Confirm Inclusion/Exclusion Criteria		X															
ATHF		X															
CIRS-G		x															
Expectations for Adherence		X															
Height		X															
Weight		X						X						X	X	Х	Х
Saliva sample for genetic testing		X															
Extra Local MADRS ifstart of treatment >2 weeks since Central MADRS			х						X								
MINI Modules A&C (Depressive and Manic Episodes)		X															
DAST-10 (if indicated by pre-screen)		X															
AUDIT (if indicated by pre-screen)		X		х	х	х	х	х		х	х	х	х	х			
Side Effect Assessment		х		х	х	х	х	Х		х	х	Х	х	х	X**	X**	X**
Adherence				х	х	х	х	Х		х	х	Х	х	х	X**	X**	X**
Falls and fall-related injuries		X		Х	х	Х	Х	Х		Х	Х	Х	Х	Х	X**	X**	X**

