NIH Toolbox Cognition and Motor batteries -@done if participant able to be seen in person		х						Х						х			х
Cognition battery including Attention/exec function (flanker and dimsional change card sort), Episodic memory (Picture seq memory), working memory (List sorting), Processing speed (pattern comparison). Baseline only: Language (Oral reading recognition) Motor battery including Dexterity (pegboard), Strength (using grip dynamometer), Balance,																	
gait speed																	
Psychological well-being (NIH Toolbox self-report measure)		х						х						х	X	х	х
Physical Function (PROMIS)		х						х						х	Х	х	х
Social Participation (PROMIS)		х						х						х	Х	х	x
AE and SAE collection (collected anytime the event occurs)																	
Anxiety (PROMIS)		х															
Done by central rater pool at WU by phone:																	
MADRS		х						х						х	х	х	х
*Typically Week 10; or upon dropout																	
**Central rater pool will assess side effects, falls, and adherence during continuation; local s	ites can do	additional	decisi	on sup	ort cal	lls "as n	eeded	during"	this tim	ne							

F3 Baseline

- Participant signs (or returns signed) informed consent form; all elements of informed consent have been discussed and participants' questions answered.
- Local Research Team Assessments: (in person if possible; approximately 3 hours)
 - MINI MDD & Bipolar Modules
 - PHQ-9 (If more than 7 days has elapsed since the PHQ-9 was done at pre-screen.)
 - Suicide History, Risk & Protective Factors
 - Baseline Side Effects
 - Expectations for Adherence
 - Behavioral Therapy Assessment
 - Falls & Related Injuries (history)
 - Height and Weight (self-reported)
 - If indicated by pre-screen: DAST-10
 - o If indicated by pre-screen: AUDIT
 - NIH Toolbox Psychological Well Being
 - o PROMIS Physical Function
 - o PROMIS Social Participation
 - PROMIS Anxiety
 - NIH Cognition and Motor Batteries (in person assessments may be foregone for participants living in remote locations)
 - o ATHF
 - o CIRS-G
 - Medical Conditions and Medication List (study doctor to review before randomization)
 - Confirm inclusion/ exclusion criteria are met
 - Randomize participant; provide initial decision support per randomization status to participant's doctor.
- Central Rater Assessments (by phone; approximately 30 minutes)
 - o MADRS

F4 Decision Support Calls

- Every 2 Weeks During Acute Treatment: Step 1 Weeks 2, 4, 6, 8, 10* & Step 2 Weeks 2, 4, 6, 8, 10*

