2.2.2. Hypothesis

Theme 1: Benefits and risks of antidepressants: outcomes that matter for patients and clinicians

- 1. Effectiveness. Augmentation arms will show greater improvement than monotherapy arms for effectiveness outcomes.
 - a. Wellness outcome: Improved psychological well-being. (H1a)
 - b. Symptom outcome: Remission from depression (defined as MADRS ≤10 at Step end).
 (H1b)
- 2. Safety. Augmentation arms will have more tolerability and safety concerns (i.e., more serious adverse events) than monotherapy arms.
 - a. Serious adverse events (H2a), falls, and fall-related injuries (H2b) are the safety outcomes.

The primary analytic strategy is a test of specific treatment strategies (e.g., aripiprazole augmentation). More recently, a report on these strategies in mixed-age veterans with TRD (Mohamed et al, JAMA 2017) has suggested that augmentation approaches yield higher remission rates than does switch. The TRD field has, likewise, converged on the overarching question of whether augmentation is superior to switch, more so than the specific question of which augmentation approach is superior (e.g., Ruberto, Jha, & Murrough, "Pharmacological treatments for patients with treatment-resistant depression", Pharmaceuticals 2020; Voineskos, Daskalakis & Blumberger, "Management of treatment-resistant depression", Neuropsychiatr Dis Treat 2020) with a recent Cochrane systematic review (Davies et al, 2019) determining that augmentation strategies appeared efficacious while switch strategies had uncertain efficacy.

For this reason, a secondary analysis of each hypothesis will test the overall strategy of augmentation vs. switch. The two augmentation arms in Step 1 will be summed and compared to the switch arm.

Theme 2: Aging influences the balance of benefits and risks of antidepressant strategies.

3. Moderator analyses (Heterogeneity of Treatment Effect). Exploratory analysis (HT-1): Effectiveness and safety differences between treatment arms will be moderated by age. Specifically, with increasing age effectiveness differences between treatment arms will decrease, and safety differences between treatment arms will increase. In addition, the following potential moderators will be assessed: executive function, co-morbid medical burden, co-morbid anxiety, and degree of treatment resistance.

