3.2. Randomization

Randomization of participants will be implemented in REDCap, using a randomized block design by alternating blocks of 3 and 6 within strata by site (i.e., St Louis vs. Pittsburgh), referral source (primary care vs. specialty mental health) and age (<70 vs >70).

Only assessors of outcome measures will be blinded. Assessors will be instructed to not ask, and participants instructed to not share the treatment to which they were assigned. Participants, providers, and other research staff will not be blinded to treatment conditions.

In this pragmatic design where all levels of adherence are allowed, participants will be considered randomized assuming they meet the eligibility requirements at screening (including any safety screens as applicable) and they have been given a randomization assignment (i.e., even if participants never took a dose of the randomized medication, they will be included in the analysis).

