6.1.2. Outcome measurements

H1a outcome will be measured by NIH Toolbox (Psychological Well-being), and the secondary outcome will be measured by PROMIS (Physical function, Social participation).

H1b outcome will be assessed by independent (blind) raters via phone interview to assess the MADRS score.

H2a outcome will be measured when SAE occurs.

H2b outcome will be assessed by independent raters.

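### SAP 6.3 lets a local MADRS replace a missing central rating at Step end without requiring a blind rater, so blinding is not secured for those remission (H1b) scores

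*SAP*

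**What the plan says.** SAP 2.2.2 defines H1b remission as a MADRS of 10 or less at Step end, and SAP 6.1.1 lists it among the primary outcomes. On who rates it, SAP 6.1.2 states: "H1b outcome will be assessed by independent (blind) raters via phone interview to assess the MADRS score". The protocol's outcome table (C4) agrees: "Assessed by independent (blind) rater via 20-30 minute phone interview". The schedule (Protocol F2) places the MADRS under the block headed "Done by central rater pool at WU by phone", and Protocol F5 lists the Step-end MADRS only among the central rater's assessments.

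SAP 6.3 then gives a specific rule for a MADRS missing at baseline or endpoint: "for those missing a centrally-administered MADRS, we will accept a locally administered one". The same paragraph says that completers still lacking a score are imputed, and that people who stop a step before week 10 with no MADRS are counted as non-remitters.

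On blinding in general, SAP 3.2 and Protocol D2 (1.g) blind only the outcome assessors. SAP 3.2 continues: "Participants, providers, and other research staff will not be blinded to treatment conditions".

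**The concern.** The MADRS is a clinician-rated scale cut at a threshold, so a shift of a point or two near 10 changes a participant's status. In a trial where participants and clinicians know the treatment, the blind central rater is the main protection for this outcome. SAP 6.3 allows a score from outside that arrangement into the same variable. It does not require the substitute rater to be blind, say how close to Step end the rating must be, mark the score, or plan an analysis without it.

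If the substituted ratings lean towards one arm, or are obtained more often in one arm, the remission comparison absorbs the difference and a reader of the results could not see it.

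**Working it through.** **1. Who gives a local rating.** Protocol F3 puts randomization and the first assignment-based decision support in the local team's list. Protocol F4 has the same team make the two-weekly calls on symptoms, side effects, adherence and dose recommendations. The local team therefore knows the assignment. No section states the blinding status of the individual who gives a local MADRS.

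**2. Where a local Step-end score would come from.** The schedule's only local MADRS is the line "Extra Local MADRS ifstart of treatment >2 weeks since Central MADRS", marked at week 0 of Step 1 and of Step 2. None is marked at Step end. A local endpoint score thus has no scheduled source and no defined window.

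**3. What the SAP 6.3 rules do to H1b.**

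| Central score at Step end | Local score | Stopped before week 10 | Completed the step |
|---|---|---|---|
| present | any | central score decides | central score decides |
| missing | 10 or less | remitter | remitter |
| missing | above 10 | non-remitter | non-remitter |
| missing | none | non-remitter by rule | imputed |

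For early stoppers without a central score, the default is non-remitter and a local score can move them only towards remission. Both the rating and the decision to obtain one can therefore set the outcome. Early exit for tolerability is expected (Protocol D2 1.j and E 1.a), and SAP 2.2.2 hypothesizes more tolerability problems with augmentation. Exposure to this rule could differ by arm, though the documents do not show that it does.

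**4. Which analyses are touched.** The H1b model in SAP 6.2 has age group and treatment, with site as strata, and no baseline MADRS. Only endpoint substitution enters H1b directly. Baseline substitution affects MADRS change and response, which SAP 6.1.1 classes as secondary.

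**5. Whether planned sensitivity analyses reach it.** Those in SAP 6.3 vary the assumptions about missing data. Once a local score is accepted, the outcome is no longer missing, so they leave it in place.

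**6. The plan's own figures.** Protocol H2 gives detectable remission differences around 40%. With a two-sided two-proportion z test, se0 = √[2p̄(1−p̄)/n], se1 = √{[p1(1−p1)+p2(1−p2)]/n}, power = Φ[(d − z·se0)/se1], and 40% as the lower rate:

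- Step 1 (500 per arm, α = .05/3): 10.17 and 11.55 points at power .8 and .9. Stated: 10.2 and 11.5.
- Step 2 (400 per arm, α = .05): 9.84 and 11.39 points. Stated: 9.8 and 11.4.

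The figures reproduce and are not in dispute. The same test is used next.

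**7. Illustrative size.** Let f be the share of endpoints that are local and b the change in the chance of being rated remitted among them. The bias in the difference between arms A and B is f_A·b_A − f_B·b_B. With the same share f in both arms this is f × (b_A − b_B), share times net shift. The documents give neither quantity. Assumed here: f of 5–20% and a net shift of 10–20 points. The rejection rate is for one pairwise test at .05/3 = .0167, with true remission of 40% in both arms. The current Step 1 size is taken as (708 − 123)/3 = 195 per arm, from SAP 3.3 and equal allocation.

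| f | net shift | bias | rejection rate, 195 per arm | rejection rate, 500 per arm |
|---|---|---|---|---|
| 5% | 10 pts | 0.5 pts | .017 | .018 |
| 10% | 10 pts | 1.0 pts | .019 | .022 |
| 10% | 20 pts | 2.0 pts | .026 | .041 |
| 20% | 20 pts | 4.0 pts | .056 | .133 |

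Last row at 195 per arm: p̄ = .42, se0 = √(2 × .42 × .58/195) = .0500, se1 = .0499, z = 2.394. Then Φ[(.04 − .1196)/.0499] + Φ[(−.04 − .1196)/.0499] ≈ .055 + .001 = .056.

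**The case against.** The strongest reply is that a reader might infer from SAP 6.3 that unblinded staff supply the primary outcome and that the blinding of remission is broken. The documents do not go that far. Both say outcome assessors are blinded, and SAP 3.2 adds that assessors do not ask about treatment and participants are told not to reveal it. Whoever gives an endpoint MADRS could be held to fall under that rule. Protocol F3 and F4 describe what a team does, not what one rater knows. This part of the objection stands, and the point is limited to blinding that is not required or documented for the substituted scores.

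A reader might also infer that the Step 2 week-0 rating would serve as the Step 1 endpoint. Its trigger counts time since a central MADRS, so it presupposes the score whose absence calls for a substitute. That reading fits poorly. What is supported is that the source is undefined.

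Third, similar use and similar shifts in both arms would largely cancel, and the middle case above (10%, 10 points) barely moves the error rate. That is correct, and it limits the severity.

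Fourth, making central-only scores the main analysis would discard observed ratings. Through the early-stopper rule it could also turn people with a local score of 10 or less into non-remitters. This is a fair reason to place central-only beside the main result rather than in its stead.

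The reply that SAP 6.3 already promises missingness checks and sensitivity analyses does not stand, because they do not separate local from central ratings.

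**Conclusion.** The concern holds in a limited form. SAP 6.1.2 and SAP 6.3 are not reconciled, and nothing in the plan secures or checks blinding for local endpoint scores used in H1b. The 0.5–4 point range rests wholly on the assumed share and net shift. Even its upper end is below the 10-point difference that Protocol H2 treats as clinically meaningful. The documents do not establish that any bias occurred or that its direction favours a particular arm. The gap is worth closing because remission is a primary outcome, the early-stopper rule makes a local score decisive for some participants, and the check uses data already held.

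**What to change.** In SAP 6.3:

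1. Accept a local endpoint MADRS only from a rater blind to assignment and within a stated window of Step end.
2. Flag every local endpoint score and report the number by arm and step, separately for early stoppers and completers.
3. Prespecify an H1b analysis that uses central blinded ratings only and treats local-only endpoint scores as missing. Handle them by multiple imputation and, separately, as non-remitters, and report both beside the main result. The second version applies the existing early-stopper default to every local-only score, so it shows the furthest that those scores could have raised remission in each arm.

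Footnote 1 of the SAP indicates that effectiveness analyses had begun when it was written. If results by arm have been seen, label the added analysis accordingly.

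Cost: SAP wording, one or two extra analyses, and slightly wider intervals in the central-only analysis. No new data or larger sample is needed. Item 1 has a further cost. If a local rater's blinding cannot be documented, the score drops out of the main analysis; an early stopper then becomes a non-remitter by rule and a completer is imputed. The counts in item 2 will show how much this matters.
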